6.5.4.	Final Report.....	21
6.5.5.	Trial Registration	21
7.	Data Ownership	21
8.	Publication Policy	22
9.	References	23

1. Protocol Summary

Title	Clinical Evaluation of Safety and Efficacy for the ClariFix™ Cryotherapy Device in Subjects with Chronic Rhinitis (FROST)
Purpose	A multi-center, prospective, non-randomized, interventional clinical trial to assess the safety and effectiveness of the ClariFix™ device when used to ablate unwanted tissue in the nose of subjects with chronic rhinitis.
Design	Prospective, non-randomized, multi-center interventional cohort
Sponsor	Arrinex, Inc.
Study Device	ClariFix™ Cryotherapy Device
Enrollment	Up to 100 subjects
Clinical Site(s)	Up to 7 sites
Study population	Subjects that suffer from chronic rhinitis symptoms
Primary Endpoints	
 • Safety as assessed by the incidence of procedure- or device-related serious adverse events (SAEs) and unanticipated adverse device effects (UADEs) • Effectiveness as assessed by the change in nasal symptoms using the four-symptom rTNSS (reflective Total Nasal Symptom Score) at 90 days post-treatment
Secondary Endpoints	
 • Incidence of device or procedure related adverse events • Impact on quality of life assessed by the Rhinoconjunctivitis Quality of Life Questionnaire (RQLQ) at 90 days post-treatment

Investigator Protocol Signature

1. I understand this protocol contains information that is confidential and proprietary to Sponsor.
2. Any additional information added to this protocol is also confidential and proprietary to Sponsor and must be treated in the same manner as the contents of this protocol.
3. I have read the entire protocol.
4. I understand what the protocol asks me to do as an Investigator.
5. I will conduct this study following this protocol and will make a reasonable effort to complete the study in the time noted.
6. I will provide this protocol to study staff under my supervision. My study staff will keep the protocol and associated documents confidential.
7. I will discuss this information with the study staff to ensure they are fully informed about the study and the ClariFix device.
8. I will not start enrolling in this study until it is approved by a governing Institutional Review Board.

1.1. Background

Rhinitis is a very common condition throughout the world. In the United States alone, it affects 10-30% of the adult general population. This accounts for 30-60 million people in the United States and the prevalence has been increasing in recent decades, making it the fifth most common chronic disease in the US. Rhinitis is the inflammation of the nasal mucosa affecting patients with at least one of the following distressing symptoms: nasal congestion, rhinorrhea, sneezing, and nasal itching.

The current standard of care to control this disease starts with pharmacologic interventions, typically beginning with over the counter medications. Nasal steroids (i.e. Flonase, Nasonex) and oral anti-histamines (i.e. Claritin, Allegra, Zyrtec) are the mainstays of medical management. They have their challenges, however, as they require daily use and have limited effectiveness, especially against non-allergic rhinitis. Sedating anti-histamines such as Benadryl are used intermittently but the somnolent side effects are not usually well tolerated.

Prescription medications are used when OTC medication management fails. Oral steroids can be effective in the short term but carry more severe long-term side effects including immunosuppression, osteoporosis, Cushing syndrome and diabetes. Adrenergic agents such as Afrin are effective but quickly result in tolerance and “rebound” (recurrence and sometimes worsening of symptoms when off the medication).

When pharmacological treatments do not provide adequate response, surgical techniques have also been developed to treat rhinitis. These techniques include electrocautery, chemocautery, laser cautery, microdebrider turbineoplasty, radiofrequency ablation, subtotal turbinectomy, total inferior turbinectomy, and submucosal resection. These procedures primarily seek to address the nasal obstructive component through reduction of the inferior turbinate.

Use of various cryosurgical tools for destruction of tissue in the nasal passageway to treat nasal obstruction or symptoms of rhinitis have been reported in the literature.^(1,2,3,4,5,6,7,8,9,10,11) Target nasal passageway locations that were subjected to cryosurgery included the nasal soft tissue covering the turbinates, which included nasal nerves. All studies included patient-reported outcomes of nasal symptoms, which is a commonly accepted method for demonstrating the effectiveness outcomes in the nasal passageway. Physicians also performed visual assessments of nasal congestion and recorded the presence of complications including resolution of any adverse symptoms. Although published reports reflect improvement in symptoms and a low rate of complications, endoscopic cryotherapy techniques and tools have not been fully optimized to achieve consistent outcomes.

Arrinex, Inc. has developed a novel cryotherapy device designed specifically to facilitate a transnasal approach to allow cryoablation of unwanted tissue in the nasal passageway.

1.2. Report of Prior Investigations

A pilot clinical study was performed to evaluate the performance of the ClariFix device as a cryosurgical tool to treat subjects with chronic rhinitis. This study was a prospective, multi-center, single-arm interventional study of the ClariFix device. The study protocol was reviewed and approved as a non-significant risk study by Quorum Review IRB. Three investigational sites were selected in the United States. All treatments were performed on consented awake subjects in an office setting by experienced otolaryngologists. Subjects were seen in the office at 7, 30, and 90 days post-treatment for follow-up assessments. Extended follow-up to a maximum of one-year post-treatment was conducted to assess the durability of treatment outcomes. The primary safety endpoint for the study was the frequency of serious device or procedure-related adverse events (SAEs). The primary efficacy endpoint was the change in subject reported nasal symptoms at the follow-up intervals relative to baseline. Nasal symptoms were assessed using the reflective Total Nasal Symptom Scale (rTNSS) and a Visual Analog Scale (VAS).

A total of twenty-seven (27) subjects were enrolled and received bilateral treatments. Treatments were successfully completed bilaterally with no complications in 100% of subjects (n=27) using injected or topical anesthesia in the office. Twenty-seven (27) subjects completed 1-month follow-up and twenty-four (24) subjects completed 90-day follow up (3 subjects were lost-to-follow-up). Twenty-four (24) subjects participated in extended follow-up. Nasal symptoms assessed by rTNSS were significantly reduced at each follow-up interval compared to baseline. The average rTNSS score was reduced by 58% from 6.2 at baseline to 2.6 at 30 days and maintained at 2.7 at 90 days (56% reduction). Extended follow-up data showed sustained improvements, with an average rTNSS of 2.3 at 180 days post-treatment. Eighty-one percent (22/27) of subjects had at least a one-point improvement of rTNSS scores at 30 days and 79% (19/24) of subjects had improved rTNSS scores at 90 days. The VAS symptom data similarly demonstrated significant reductions in nasal symptoms. The average total VAS score was reduced by 50% and 53% at 30 and 90 days, respectively. There were no device or procedure-related serious adverse events or unanticipated adverse device effects reported during the course of the study.

In this pilot study of 27 subjects, office-based treatment using the ClariFix device was demonstrated to be safe, well-tolerated, and effective in reducing nasal symptoms in subjects with chronic rhinitis. This study will build on those results and is designed to assess the safety and effectiveness of the ClariFix device when used to ablate unwanted tissue in the nasal passageway of subjects with chronic rhinitis.

1.3. Device Description

The ClariFix device is a handheld cryosurgical device which provides focal, controlled freezing to the target tissue. In order to deliver treatment, a nitrous oxide canister is inserted into the device. The device's cryoprobe is placed in contact with the target tissue, under direct visualization. The low profile semi-flexible cannula allows the user to maintain visibility of the

cryoprobe and apply pressure to target tissue with the cryoprobe to ensure contact throughout the treatment. Once the cryoprobe is in the desired position, the physician manually initiates the flow of cryogen and ablates unwanted tissue. The nitrous oxide gas is contained within the cryoprobe and allowed to exit the device at the handle away from the subjects.

The sterile device is provided with two 10-ml non-sterile cryogen cannisters. The cryogen canisters are provided separately. The canisters contain enough cryogen for 60 seconds (10-ml) of ablation time.

The ClariFix device consists of a Cryoprobe, Cannula, On/Off valve, Handle, & Cap. The device is provided sterile and designed for single patient use.

[figure not shown]

Figure 1. ClariFix™ Device

1.4. Regulatory Status

The ClariFix™ device (K162608) is an FDA 510(k) cleared Class II cryosurgical tool indicated for the destruction of unwanted tissue during surgical procedures, including in adults with chronic rhinitis.

2. Risk/Benefit Analysis

The Sponsor has undertaken a comprehensive risk-benefit analysis.

2.1. Benefits

Use of the ClariFix device as a tool during cryosurgery may reduce the symptoms of chronic rhinitis. Improvement in rhinitis symptoms may improve patients' quality of life and may improve work or school productivity. This study may provide valuable information as to the underlying mechanisms of rhinitis, which may enable the development of more effective devices in the future.

2.2. Risks

The study procedure involves transnasal placement of the ClariFix device under endoscopic visualization and use of local anesthesia. In order to minimize risks associated with the study, the procedure will be performed by practicing otolaryngologists experienced in transnasal procedures. Further, subjects with known allergies to local anesthetic agents shall be excluded from participation in the study.

While nasal endoscopy is generally known to be safe, anticipated risks may include, but are not limited to:

- Temporary pain, discomfort or irritation
- Bleeding
- Cerebrospinal fluid (CSF) leak

Similarly, while generally known to be safe, submucosal placement of a needle and delivery of local anesthesia may be additionally associated with the following risks, not limited to:

- Minor bleeding
- Pain with injection
- Facial numbness or tingling
- Sedation
- Tachycardia, nervousness, anxiety
- Lightheadedness, dizziness, confusion,
- Muscular twitching, tremors
- Infection
- Allergic reaction
- Lidocaine or Tetracaine toxicity with overdose
- Visual disturbance
- Vomiting
- Headache
- Tinnitus
- Seizures
- Hypotension, bradycardia
- Unconsciousness
- Respiratory arrest
- Cardiac arrest

In addition, the specific nature of cryosurgery using the ClariFix Device results in a known potential for adverse events related to the cold application, including but not limited to:

- Bleeding
- Crusting and/or tissue sloughing

- Swelling
- Pain/discomfort and/or facial pain
- Sensory alterations (numbness, tingling) in the face/mouth
- Increase in nasal congestion, Intranasal scarring/nasal obstruction
- Headache
- Dry nose
- Ear blockage
- Septal perforation
- Dry eyes, optical changes or orbital damage
- Vasovagal reaction
- Infection

3. Study Protocol

3.1. Design

Prospective, non-randomized, multi-center interventional cohort.

3.2. Study Duration and Timeline

Enrollment and follow-up is expected to take 36 months. The anticipated timeline is:

- Actual start date: March 2017
- Anticipated end date: March 2020

3.3. Physician Participants

Study investigators must be practicing physicians in otolaryngology.

3.4. Site Requirements

Site investigators must have at least one study coordinator with experience in conducting clinical research and with sufficient time to conduct the study.

3.5. Subject Recruitment

Subjects who seek treatment of chronic rhinitis will be recruited from the general population.

3.6. Sample Size

The target sample size is 100 treated subjects.

3.7. Subject Eligibility

To be eligible to participate, subjects must meet all of the inclusion criteria and none of the exclusion criteria listed in **Table 1**.

Table 1. Eligibility Criteria

Inclusion Criteria
 
 a) Subject is ≥ 21 years of age b) Subject has moderate to severe symptoms of rhinorrhea (individual symptom rating of 2 or 3), mild to severe symptoms of congestion (individual symptom rating of 1, 2 or 3) and a minimum rTNSS score of 4 (out of 12) at the time of the treatment visit. These symptoms shall have been present for > 6 months. c) Subject has had documented allergy test within the last 10 years that defines whether or not subject has allergies to perennial and seasonal allergens or is willing to have one performed prior to study exit. d) Subject has been dissatisfied with medical management, defined as usage of intranasal steroids for a minimum of 4 weeks without adequate symptom relief by the subject's assessment e) Subject has signed IRB-approved informed consent form

Exclusion Criteria
 
 a) Subject has clinically significant anatomic obstructions that in the investigator's opinion limit access to the posterior nose, including but not limited to septal deviation or perforation, nasal polyps, sinonasal tumor. b) Subject has had any prior sinus or nasal surgery that significantly alters the anatomy of the posterior nose. c) Subject has active nasal or sinus infection d) Subject has moderate to severe ocular symptoms e) Subject has a history of nosebleeds in the past 3 months f) Subject has a history of rhinitis medicamentosa g) Subject has had prior head or neck irradiation h) Subject has active coagulation disorder or is receiving anti-coagulants which cannot be safely stopped for 4 weeks (excluding aspirin) i) Subject is pregnant j) Subject is participating in another clinical research study k) Subject has an allergy or intolerance to anesthetic agent

- l) Subjects with cryoglobulinemia, paroxysmal cold hemoglobinuria, cold urticaria, Raynaud's disease, and/or, open and/or infected wounds at or near the target tissue
- m) Any physical condition that in the investigator's opinion would prevent adequate study participation or pose increased risk

3.8. Screening Procedures (Visit 1)

The screening evaluation will take place up to 30 days prior to the study procedure. Potential study subjects will be pre-screened against study eligibility criteria, including confirmation of prior allergy test (if none, an allergen-specific IgE antibody blood test will be required). Endoscopic assessment will be performed to evaluate anatomic suitability, and photographic and/or video documentation will be obtained if possible.

A member of the site's Research Team will explain the study to the subject and seek the subject's written informed consent. The subject must sign the consent form prior to enrollment. This form must have prior approval of the Institutional Review Board (IRB).

All female subjects of childbearing potential will be asked if they are pregnant at the screening visit. If the subject is pregnant, they will be excluded from participation.

The investigator and/or designee will document the subject's medical information and endoscopic observations on the Screening Case Report Form (CRF), as well as subjective assessment of nasal symptoms using the rTNSS (reflective Total Nasal Symptom Score) described in Section 3.11.3.

At the time of the screening visit, subjects will report any prior and/or ongoing use of any nasal sprays. Subjects will also be instructed not to take nasal anticholinergic sprays (e.g., Atrovent) beginning a minimum of 3 days prior to the procedure and throughout their study participation (See Section 3.12). Subjects may continue to use other nasal medications, but will be instructed not to introduce any new category of nasal sprays into their medication regimen for the duration of their study participation (changes in medication brand are acceptable).

Subjects will be instructed not to take anti-coagulant medications for 2 weeks prior to the procedure, and 2 weeks after the procedure.

3.9. Study Treatment (Visit 2)

The study treatment is described below. Further details can be found in the instructions for use document.

3.9.1. Pre-Procedure Evaluation

The baseline evaluation will take place on the day of the study procedure. All female subjects of childbearing potential will be asked to take a pregnancy test (urine). If the subject is pregnant,

they will not be considered eligible to participate in the study. If a subject becomes pregnant after the study treatment, during the study follow-up period, the subject shall be withdrawn from the study and will not undergo any further testing. The subject will be asked to rate their nasal symptoms using the rTNSS. If the subject does not meet the minimum symptom score requirement (**Table 1**, Inclusion criterion b), the subject will not be considered eligible to participate in the study.

If all the eligibility criteria are met, and the subject has signed the IRB-approved informed consent document, the subject shall be considered enrolled. The investigator and/or designee will document the subject's medical information on the Baseline CRF. Subjects will also complete the quality of life questionnaire (RQLQ) described in Section 3.11.4. Subjects shall then undergo treatment with the study device.

3.9.2. Preparation for Procedure

The subject will be positioned in an upright or partially reclined sitting position. The subject will then undergo appropriate local anesthesia procedure, per physician preference. Baseline images of the intended treatment sites will be collected endoscopically whenever possible.

3.9.3. Cryotherapy Procedure

Video documentation including recording of intra-procedural endoscopic visualization as well as external video documentation of the procedure may be performed. Subject pain/discomfort during each treatment will be assessed using Wong-Baker FACES pain scale (See Section 3.11.2).

Details of use of the ClariFix device are provided in the IFU (Instructions For Use). Use of the device in the nasal passageway for the purpose of this study involves the following:

- a. Prepare the device per the IFU. Insert cryogen canister into handle.
- b. An endoscope will be placed into the nasal cavity to allow visualization of the cryotherapy procedure.
- c. Insert the cryoprobe into the nasal cavity, and advance until the cryoprobe is located at the posterior aspect of the middle turbinate meatus.
- d. Place the cryoprobe against the mucosal surface. Visually inspect that the probe is against the lateral wall and the lower 1/3 of the cryoprobe is laying on the inferior turbinate at the desired location in the treatment zone. Ensure the cryoprobe is in firm contact by gently rotating the device cannula toward the lateral wall (clockwise for the subject's left nasal cavity treatment, counterclockwise for the right).

[figure not shown]

Figure 2. Treatment Location

- e. Obtain photographic and/or video documentation if available.
- f. Activate cryotherapy delivery via the valve on the device handle.
- g. Maintain the device in position for the duration of the cooling cycle (up 1 minute for the 10-ml and 2 minutes for the 21-ml).
- h. Once cooling cycle is complete, allow cryoprobe to thaw and then withdraw the cryoprobe from the nasal cavity.
- i. Evaluate the treatment site with the endoscope and obtain photographic and/or video documentation if possible.
- j. If a second cooling cycle is desired, replace the cryogen canister per the device IFU and repeat steps a to i. Up to two cooling cycles may be performed in each nasal cavity.
- k. Rotate cannula and perform the identical procedure in the contralateral nasal cavity.

In this study, the targeted treatment regimen is:

- Application of cold in each treatment cycle for up to 120 seconds
- Treatment to approximately -20°C at a depth of 3 millimeters and -60 to -80 °C at the surface of the cryoprobe)

The investigator or study coordinator will record treatment data on the Procedure CRF. Additionally, physicians' feedback on device usability and ease of treatment delivery will be recorded at the time of the Procedure Visit.

Note: All subjects should have bilateral treatment. Unilateral treatment will be considered incomplete. Subjects who receive an incomplete treatment will receive all follow up evaluations per protocol.

3.9.4. Post-Procedure

After the procedure, the treatment area will be evaluated endoscopically. The subject will be instructed in post-treatment care. The subject will also be told to report any adverse events to the Investigator.

3.10. Follow-up Procedures

Subjects will be evaluated immediately post-treatment, at 1-day post-treatment by phone, and at 7, 30, 90, 180, 270, and 365 days post-treatment by office visit, (see **Table 2**). In addition, subjects participating in the Extended Follow-up (See Section 3.10.5) will be evaluated at 15, 18, 21 and 24 months post-treatment by office visit or via [contact]-Day Phone Evaluation (Visit 3)

A study team member will telephone the subject one (1) day (+2 days) following the procedure visit. The 1-day phone evaluation will consist of assessment of any study-related adverse events.

3.10.2. 7-Day Follow-Up (Visit 4)

Subject will return to the office seven (7) days (\pm days) following the procedure visit.

The subject will be assessed for Adverse Events and Concomitant Medications will be updated.

If deemed necessary by the Investigator, an endoscopic exam may be performed (See Section 3.11.1).

3.10.3. 30- and 90-Day Follow-Ups (Visits 5 & 6)

Subject will return to the office at thirty (30) days (± 7 days) and ninety (90) days (± 14 days) following the procedure visit.

Any adverse events will be documented, and concomitant medications will be reviewed and updated, if applicable. Overall health information will be reviewed and documented, and subject reported nasal symptoms will be recorded.

The investigator will perform an endoscopic assessment of the treatment sites (left and right) will be performed and findings documented (See Section 3.11.1).

At the 90-day office visit, a subject satisfaction questionnaire and a quality of life questionnaire (RQLQ) will be administered.

3.10.4. 180-, 270- and 365-Day Follow-Ups (Visits 7, 8 & 9)

Subject will return to the office at 180 days (± 21 days), 270 days (± 30 days), and 365 days (± 30 days) following the procedure visit.

Any adverse events will be documented, and concomitant medications will be reviewed and updated, if applicable. Overall health information will be reviewed and documented, and subject reported nasal symptoms via rTNSS scale will be recorded.

At the 180-Day office visit, the investigator will perform an endoscopic assessment of the treatment sites (left and right) and findings will be documented.

At the end of the 365-day office visit, the subject will be given the option to continue through the 24-month timepoint. If the subject does not consent to the extended follow-up, the subject's participation in the study will be complete and will be exited.

3.10.5. Extended Follow-Up: 15-, 18-, 21- & 24-Month Follow-Ups (Visits 10, 11, 12, 13)

Subjects who have consented to continue into the Extended Follow-up will complete study visits at the 15-, 18-, 21- and 24-Month (all ± 30 days) timepoints following the procedure visit. The 15-, 18-, 21- and 24-Month Follow-up visits may be complete in-office or via phone.

Any adverse events will be documented, and concomitant medications will be reviewed and updated, if applicable. Overall health information will be reviewed and documented, and subject reported nasal symptoms via rTNSS scale will be recorded.

At the 18- and 24-Month visits, the RQLQ will be administered.

At the completion of the 24-Month visits, study participation will be complete.

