5.1.3. Exploratory Endpoints

- Effectiveness as assessed by the change in nasal symptoms using the four-symptom rTNSS (reflective Total Nasal Symptom Score) from baseline at all other follow-up points
- Treatment response as defined by $\geq 25\%$ and $\geq 50\%$ improvement in rTNSS scores
- Change in individual components of the rTNSS score
- Impact on quality of life assessed by the Rhinoconjunctivitis Quality of Life Questionnaire (RQLQ) at 18 months and 24 months post-treatment

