5.2.4. General Analytical Considerations

Continuous data will be summarized using descriptive statistics: n, mean, standard deviation, median, minimum and maximum. Continuous variables that are recorded using approximate values (e.g., $<$ or $>$) will be replaced by the closest exact value for the calculation of summary statistics. Categorical variables will be summarized using frequency counts and percentages. For ordinal-scaled variables, a combination of the above may be employed as appropriate: frequency and percentage of observations within a category and means and standard

deviations of the scores of the categories. For categorical and ordinal variables, percentages will be calculated based on non-missing data.

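### The 15-24 month results come only from subjects who chose to stay once their 365-day score was known, so they are not comparable with the earlier results from all attendees

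*Combined protocol and SAP*

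**What the plan says.** Section 3.10.4 covers the 180-, 270- and 365-day visits. At each, "subject reported nasal symptoms via rTNSS scale will be recorded". It then sets the entry rule for the later phase: "At the end of the 365-day office visit, the subject will be given the option to continue through the 24-month timepoint". For those who decline: "If the subject does not consent to the extended follow-up, the subject's participation in the study will be complete and will be exited".

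Section 3.10.5 takes the later data from consenting subjects only: "Subjects who have consented to continue into the Extended Follow-up will complete study visits at the 15-, 18-, 21- and 24-Month".

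Section 5.1.3 lists, as exploratory endpoints, the rTNSS change "from baseline at all other follow-up points" and the RQLQ "at 18 months and 24 months post-treatment". It also lists response at 25% and 50% improvement, without naming a visit.

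Three rules in Section 5.2 govern how these are computed:
- Section 5.2.3 admits a subject to the Efficacy population on the strength of any single follow-up assessment. It defines no separate cohort for the late visits.
- Section 5.2.4, for categorical and ordinal variables, states that "percentages will be calculated based on non-missing data".
- Section 5.2.5 rules out imputation and names the paired t-test and/or the Wilcoxon signed rank test.

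Nothing in Section 5.2 compares continuers with those who exit, or follows one fixed group through to month 24.

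**The concern.** When the offer is made, the subject has just rated the symptoms in an open-label study (Section 5.2.1). Where possible, the investigator has also rated improvement since treatment (Section 3.11.1). Both can know how the treatment worked before the subject decides. If the decision depends on that result, the group changes in composition between day 365 and month 15 in a way related to the outcome.

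The plan would then give visit-by-visit summaries in which the points up to day 365 come from all attendees and the points from month 15 come from volunteers. Set side by side, they would look like one time course. A stable or improving late mean could coexist with real waning, or a falling one with none, and no planned table would show which.

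This differs from ordinary missed visits. The protocol itself creates the break, at a known time and after the outcome has been observed.

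**Working it through.** **The plan's own figure.** The documents state no figure for the extended phase. The only one nearby is the 90-day sample size in Section 5.2.6: SD 2.5, difference 1, two-sided alpha 0.05, 90% power. With the noncentral t distribution, power is 0.897 at n = 67 and 0.902 at n = 68, so the stated 68 is reproduced. The present point does not touch it.

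**Inputs for the illustration.**
- Proportion improved: r = 19/24 = 0.792 (pilot, 90 days, Section 1.2).
- Mean change: 2.7 - 6.2 = -3.5 (pilot, 90 days, Section 1.2).
- Assumed: not-improved subjects have change 0, so improved subjects average -3.5/0.792 = -4.42.
- Assumed: no score changes after day 365.
- Assumed: opt-in rates a (improved) and b (not improved). The documents give none, so a range is shown.

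**Formulas.** Proportion improved among continuers: p = r·a / [r·a + (1 - r)·b]. Mean change among continuers: p × (-4.42).

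Example for a = 0.8, b = 0.5: r·a = 0.633, (1 - r)·b = 0.104, p = 0.633/0.738 = 0.859, mean = -3.80.

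| Opt-in, improved / not improved | Improved among continuers | Mean change | Shift from 79.2% and -3.50 |
|---|---|---|---|
| 70% / 60% | 81.6% | -3.61 | +2.4 pp, 0.11 favourable |
| 80% / 50% | 85.9% | -3.80 | +6.7 pp, 0.30 favourable |
| 90% / 30% | 91.9% | -4.06 | +12.8 pp, 0.56 favourable |
| 70% / 70% | 79.2% | -3.50 | none |
| 60% / 80% | 74.0% | -3.27 | -5.1 pp, 0.23 unfavourable |

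**Can it hide waning?** Suppose every subject worsens by 0.5 after day 365, so the true mean goes from -3.50 to -3.00. With 90%/30% opt-in, the continuers show -4.06 + 0.50 = -3.56, which looks stable. With 80%/50% they show -3.80 + 0.50 = -3.30, so part of the decline is hidden.

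**Sensitivity to the model.** Take instead a normal distribution of change (mean -3.5, SD 2.5) with the better and worse halves opting in at different rates. The mean among continuers is -3.5 - 2.5·√(2/π)·(a - b)/(a + b). At 80%/60% this is -3.78, and at 90%/30% it is -4.50. The size depends on how choice relates to outcome, as well as on the rates.

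**Regression to the mean.** The rTNSS is a 24-hour recall (Section 3.11.3). If choice depends on the observed day-365 score, SDs are equal and the day-365-to-late correlation is ρ, the late shift is ρ times the frozen-score value. The documents give no ρ. At ρ = 0.5, the 0.56 shift becomes 0.28 and the 0.11 shift about 0.05. In the first case, continuers would go from -4.06 at day 365 to -3.78 later, an apparent worsening of 0.28 with no true average change.

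**Same-cohort check.** With frozen scores, reporting day 365 and month 24 for the same continuers gives a shift of zero in every row of the table.

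**The case against.** The strongest case against is that the plan makes no claim this would damage. It uses the word durability only for the pilot's extended follow-up (Section 1.2). It sets no hypothesis, trend test or month-12-to-24 comparison, and the stated hypothesis and power concern 90 days. The late endpoints are exploratory. Each continuer is compared with their own baseline, which is valid for continuers, and Section 5.2.4 reports n with each continuous summary, so the smaller group would be visible.

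Most of this stands and limits the point. It does not remove it. Pairing with baseline does not make continuers comparable with all day-365 attendees, and n shows how many left but not who. Repeated rTNSS to month 24, tabulated by visit, invites reading as one course whether or not a test is attached.

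Four stronger readings are tempting and not supported:
- A reader might infer that satisfied subjects will stay more often and that the late results will be flattering. No document says so, and the table shows zero and reversed shifts.
- A reader might take the non-missing rule to govern everything. It covers percentages only. For mean change, the argument rests on the no-imputation rule in Section 5.2.5.
- A reader might take 79% as the trial's responder rate at one year. It is the pilot's 90-day share with improved scores, not a 25% or 50% response. The -3.5 is a difference of group means that may rest on different subjects, since 27 enrolled and 24 reached day 90.
- A reader might take change from day 365 as the cleanest durability estimate. It is open to regression to the mean, and the RQLQ has no day-365 value (Section 3.11.4 and Table 2).

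**Conclusion.** The concern holds as a matter of comparability. As written, the plan draws its 15-24 month results from a self-selected subset, formed after the 365-day outcome is known, and provides nothing to separate a change in composition from a change in subjects.

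Under the two-group illustration, the shift is about 0.1-0.6 points in mean change and about 2-13 percentage points in the proportion improved, favourable if improved subjects stay more often. For scale, the trial is sized to detect one point. These figures rest on assumed opt-in rates, pilot 90-day values and frozen scores. They show the mechanism and do not forecast the trial. Direction and size are unknown.

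Only exploratory endpoints are involved. The 90-day primary and secondary endpoints and the 68 evaluable subjects stand. Offering the extension as an option is legitimate and need not change.

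**What to change.** Add to Section 5.2.5, for the exploratory late endpoints:

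1. Present the continuers' own time course. For rTNSS: baseline, day 90, day 365 and each later visit. For RQLQ: baseline, day 90, 18 months and 24 months. Base any statement on durability on this course, not on continuers set against all earlier attendees. Within-subject change from day 365 may be shown beside it for rTNSS, with a note that selection on the day-365 score can cause regression to the mean.
2. Tabulate baseline, day-90 and day-365 rTNSS for subjects who continued and subjects who exited.
3. Optionally, as a labelled sensitivity analysis, give late responder rates with all treated subjects as the denominator, counting those without late data as non-responders. This is a form of imputation, so the no-imputation sentence in Section 5.2.5 must be amended to allow it. It is a floor, not an estimate, because it counts as failures subjects who completed the planned year.

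The cost is a paragraph of analysis text and a few tables from data already collected, with no new visits or subjects. Late figures may look less favourable.
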